3.3 Populations for Analyses

For the purposes of analysis, the following analysis sets will be defined:

Participant Analysis Set	Description
Enrolled	All participants with data in the CRF. Note: the study groups are not randomized. The study groups are determined based on age. However, a subset of participants from each age group will be randomly selected in order for their blood to be tested using the SN method.
Safety Analysis Set (SafAS)	Participants who have received one dose of the study vaccine.
	Safety data recorded for a vaccine received out of the protocol design will be excluded from the analysis (and listed separately).
Full analysis set (FAS)	Subset of participants who received one dose of the study vaccine and had a post-vaccination blood sample.
	For the assessment of the immune response by SN assay, the analysis will be performed on the participants from FAS who were randomized in the exploratory subset (FAS-SN).

Per-protocol analysis set	Subset of the FAS. Participants presenting with at least one of the	
(PPAS)	following criteria will be excluded from the PPAS:	
	Participant did not meet all protocol-specified inclusion criteria or met at least one of the protocol-specified exclusion criteria	
	· Participant did not receive vaccine in the proper time window	
	· Preparation and / or administration of vaccine was not done as per-protocol	
	Participant did not provide the post-dose serology sample at V02 in the proper time window ([D26, D39]) or a post-dose serology sample was not drawn	
	Participant received a protocol-prohibited medications impacting or that may have an impact on the immune response	
	Any other deviation identified during the study conduct and identified as relevant by the clinical team during data review, ie, indicated as excluding subjects from this analysis set in the manual deviations dataset. This will be limited to exceptional circumstances given the open-label nature of the trial.	
	For the assessment of the immune response by SN assay, the analysis will be performed on the participants from PPAS who were randomized in the exploratory subset (PPAS-SN).	

SAP Core Body: VAP00027

3.4 Statistical Analyses

3.4.1 General Considerations

All statistical analyses will be performed under the responsibility of the Sponsor's Biostatistics Platform using the SAS® software, Version 9.4 or above (SAS Institute, Cary, North Carolina, USA).

For descriptive purposes, the following statistics will be presented:

Table 3.1: Descriptive statistics produced

Disposition and follow-up description	Categorical data	At least number of participants (Percentage of participants are also possible).
	Continuous data	Mean, standard deviation, minimum and maximum.
Baseline	Categorical data	Number of participants.
characteristics		Percentage of participants.
	Continuous data	Mean, standard deviation, quartiles, minimum and maximum.
Clinical safety results	Categorical data	Solicited: Number and percentage (95% confidence intervals [CIs] for main endpoints) of participants.

		Unsolicited: Number and percentage (95% CIs for main endpoints) of participants and number of events.
Immunogenicity results	Categorical data (seroconversion, cutoff)	Number and percentage (95% CIs for main endpoints) of participants.
	Continuous data (titer / concentration)	Log10: Mean and standard deviation. Anti-Log10 (work on Log10 distribution, and anti-Log10 applied): Geometric mean, 95% CI of the geometric mean, quartiles, minimum, and maximum. Graphical representation by Reverse Cumulative Distribution Curve (RCDC).

SAP Core Body: VAP00027

The CI for the single proportion will be calculated using the exact binomial method (Clopper-Pearson method, quoted by Newcombe (1), ie, using the inverse of the beta integral with SAS®.

For immunogenicity results, assuming that \log_{10} transformation of the titers / data follows a normal distribution, at first, the mean and the 95% CI will be calculated on \log_{10} (titers / data) using the usual calculation for normal distribution (using Student's t distribution with n-1 degree of freedom), then antilog transformations will be applied to the results of calculations, in order to provide geometric means (GMs) and their 95% CI.

3.4.2 Primary Endpoints

The immunogenicity parameters will be calculated in each study group with their 95% CIs using the exact binomial distribution (Clopper-Pearson method) for proportions and using normal approximation of log-transformed for GMTs and GMTs ratio.

Statistical methodology for analyzing the 8 primary endpoints (GMTs and SC rates).

NI of RIV4 in participants aged 9 to 17 years vs participants aged 18 to 49 years will be conducted for GMTs and SC rates.

For each strain, the NI methodology will be applied to compare the post-vaccination GMTs and the SC rates between the groups using a 1-sided Type I error rate of 0.025 with the given individual hypothesis.

The primary analysis will be conducted in 2 steps starting with testing for NI of GMTs between the age group 9-17 years and the age group 18-49 years. If NI of GMTs based on the 4 strains is demonstrated, then NI of the SC rates will be also tested.

Step 1: Geometric Mean Titers

Assuming that log_{10} transformation of the data follows a normal distribution, the log_{10} (data) will be used for the statistical analysis, then antilog transformations will be applied to the results of calculations, in order to provide the results in terms of geometric means (GMs).

The statistical methodology is based on a 2-sided 95% CI of the ratio of the GMTs (RIV4[9-17y] divided by RIV4[18-49y]) at 28 days after vaccination. NI for GMTs is demonstrated if the lower

limit of the 2-sided 95% CI of the GMT ratio is > 0.667 for each of the 4 virus strains. The 95% CI will be calculated using normal approximation of log-transformed titers.

SAP Core Body: VAP00027

Step 2: Seroconversion Rates

The statistical methodology is based on a 2-sided 95% CI of the difference in SC rates (RIV4 [9-17years] minus RIV4 [18-49years]) at 28 days after vaccination. NI for SC rates is demonstrated if the lower limit of the 2-sided 95% CI is >-10% for the 4 strains. The 95% CI of the rate difference is computed using the Wilson Score method without continuity correction. All 4 strains must demonstrate NI of the SC rate in order for study SC rates to demonstrate NI

The PPAS will be used as the primary analysis set for this objective (GMTs and SC rates).

The primary objective is successful if NI for GMTs and NI for SC rates are successful.

3.4.3 Secondary Endpoints

Immunogenicity

success.

The immunogenicity parameters will be calculated with their 95% CIs using the exact binomial distribution (Clopper-Pearson method) for proportions and using normal approximation of log-transformed for GMTs and GMTs ratio. The 95% CI of proportions difference (ie, difference between vaccine groups in SC) will be calculated using Wilson Score method without continuity correction. All analyses will be conducted by study group.

The following descriptive statistics will be displayed:

- GMTs of individual-HAI titer on D01 and 28 days after vaccination (D29)
- Percentage of participants with detectable HAI titer, ie, with a titer ≥ 10 (1/dil) at D01 and 28 days after vaccination (D29)
- GMs of individual titer ratio: 28 days after vaccination (D29) /D01
- Percentage of participants with titer ≥ 40 (1/dil) on D01 and 28 days after vaccination (D29)
- SC rates (titer < 10 [1/dil] at D01 and post-injection titer ≥ 40 (1/dil) at D29 or titer ≥ 10 (1/dil) at D01 and a ≥ 4-fold rise in titer (1/dil) at D29)
- The RCDCs of pre-vaccination titer (D01), and post-vaccination titer (D29) will be generated for each study group. The RCDCs will include the plots of the 2 study groups the same figure.

The analysis will be conducted for each immunogenicity variable on the PPAS, and on FAS if the attrition rate from FAS to PPAS is greater than 10%.

In addition, subgroup analyses will be performed; in particular, immunogenicity will be described according to age subgroups (9-11y, 12-17y, 18-34y and 35-49y), sex, race, previous influenza vaccination status (received a seasonal influenza vaccine in the last past influenza season or not) and baseline seropositivity status (seropositive and seronegative are defined as baseline antibody titer $\geq 1:10$ or < 1:10)., as appropriate according to number of participants in the respective subgroups.

Safety

For the main safety parameters, 95% CIs of point estimates will be calculated using the exact binomial method (Clopper-Pearson method) for single proportions and using the normal approximation for quantitative data.

SAP Core Body: VAP00027

All analyses will be descriptive; no hypotheses will be tested.

The number of participants with documented safety will be used as denominator of the frequencies.

For solicited reactions, the denominator will be the total number of participants who have non-missing data for the endpoint considered

For unsolicited AEs, the denominator will be the total number of participants who were vaccinated.

SafAS will be the analysis population of safety data.

In terms of contents, solicited reactions will be presented by time to onset, maximum severity, number of days of occurrence and action taken; unsolicited AEs will be presented by causal relationship, time of onset, maximum severity and duration; SAEs will be presented by causal relationship, seriousness and outcome.

Subgroup analyses will also be performed; in particular, the main safety endpoints will be described according to age subgroups (9-11y, 12-17y, 18-34y and 35-49y), previous vaccination status, sex and race, as appropriate according to number of participants in the respective subgroups.

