The biological samples will be securely stored at the Sanofi Pasteur laboratory up to 25 years after the end of the study. Any samples remaining at the end of retention period will be destroyed. If a participant requests destruction of his/her samples before the end of the retention period, the investigator must notify the Sponsor (or its contract organization) in writing. In such case, samples will be destroyed and sample related coded data will be anonymized unless otherwise required by applicable laws.

Study participant coded data will be stored for future research for up to 25 years after the end of the study. If data are still considered of important scientific value after this period, coded data already available will be anonymized unless otherwise required by applicable laws (the same will apply to the data of a study participant who has requested the destruction of his/her samples).

Participant's coded data sets provided to researchers for a specific research project will be available to the researchers for a maximum of 2 years after the end of their specific project (end of project is defined by publication of the results or finalization of the future research project report).

Note: The other biological samples collected to qualify the participant for inclusion in the study or to monitor his/her health during the study are dedicated for immediate use. If any of these biological samples are not completely used up, they will be destroyed at the latest at the end of the study or after the time requested by local law.

9 Statistical Considerations

All statistical analyses will be performed under the responsibility of the Sponsor's Biostatistics Platform using the SAS® software, Version 9.4 or above.

The core SAP will be written and peer reviewed before the initiation of the study. In accordance with the protocol, the SAP will describe all analyses to be performed by the Sponsor and all the conventions to be taken.

For descriptive purposes, the following statistics will be presented:

Table 9.1: Descriptive statistics produced

Baseline characteristics	Categorical data	Number and percentage of participants
and follow-up description Continuous data		Mean, standard deviation, quartiles, minimum, and maximum
Safety results	Categorical data	Solicited and biological safety: Number and percentage (95% CIs) of participants
		Unsolicited: Number and percentage (95% CIs) of participants, and number of events

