9.4 Statistical Analyses

The SAP will be finalized prior to database lock, and it will include a more technical and detailed description of the statistical analyses described in this section. This section is a summary of the planned statistical analyses of the most important endpoints including primary and key secondary endpoints.

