9.4.3 Secondary Endpoints

Immunogenicity

The immunogenicity parameters will be calculated with their 95% CIs using the exact binomial distribution (Clopper-Pearson method) for proportions and using normal approximation of log-transformed for GMTs and GMTs ratio. The 95% CI of proportions difference (ie, difference between vaccine groups in SC) will be calculated using Wilson Score method without continuity correction. All analyses will be conducted by study group. The main parameters will also be described by age subgroup.

The RCDCs of pre-vaccination titer (D01), and post-vaccination titer (D29) will be generated for each study group. The RCDCs will include the plots of the 2 study groups in the same figure.

The analysis will be conducted for each immunogenicity variable on the PPAS and on FAS.

In addition, subgroup analyses will be performed; in particular, immunogenicity will be described according to age subgroups (9-11 years, 12-17 years, 18-34 years and 35-49 years), sex, race, previous influenza vaccination status (received a seasonal influenza vaccine in the last past influenza season or not) and, baseline seropositivity status (seropositive and seronegative are defined as baseline antibody titer $\geq 1:10$ or < 1:10), as appropriate according to number of participants in the respective subgroups.

Safety

For the main safety parameters, 95% CIs of point estimates will be calculated using the exact binomial method (Clopper-Pearson method) for single proportions and using the normal approximation for quantitative data.

All analyses will be descriptive; no hypotheses will be tested.

The number of participants with documented safety will be used as denominator of the frequencies.

For solicited reactions, the denominator will be the total number of participants who have nonmissing data for the endpoint considered

For unsolicited AEs, the denominator will be the total number of participants who were vaccinated.

SafAS will be the analysis population of safety data.

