9.4.4 Exploratory Endpoints

The immunogenicity parameters will be calculated with their 95% CIs using the exact binomial distribution (Clopper-Pearson method) for proportions and using normal approximation of log-transformed for GMTs. All analyses will be conducted by study group. The main parameters will also de described by age subgroup. For some parameters (eg. GMTs, 4-fold rise) difference or ratio between groups may be calculated with 95%CI. The 95% CI of ratios of GMTs will be calculated using normal approximation of log-transformed titers and those for proportions difference (ie, difference between vaccine groups in SC) will be calculated using Wilson Score method without continuity correction.

The RCDCs of pre-vaccination titer (D01) and post-vaccination titer (D29) will be generated for each study group. The RCDCs will include the plots of the 2 groups on the same figure.

The analysis will be conducted for each immunogenicity variable on the PPAS subset (PPAS-SN) and on the FAS subset (FAS-SN).

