3.2 Sample Size Determination

A total of approximately 1200 evaluable participants 9 to 49 years of age (600 children and adolescents 9 to 17 years of age [approximately 30% children 9 to 11 years of age] and 600 adults 18 to 49 years of age) will be assessed.

SAP Core Body: VAP00027

Assuming the same GMT for each strain in the age groups (9 to 17 years vs. 18 to 49 years) compared, and a standard deviation of log₁₀ titers of 0.6 with a NI margin of 1.5; NI for GMTs would be demonstrated with a power of at least 99.6%.

Assuming in each vaccine group the same expected SC rates (0.7, 0.5, 0.6, 0.5) for each of the 4 strains (A/H1N1, A/H3N2, B/Yamagata and B/Victoria), based on conservative estimates from historical data, and a NI margin of 10%, the NI for SC rate can be demonstrated with a study power of approximately 80.10% (96.66%, 93.70%, 94.38% and 93.70% for each strain, respectively).

Hence, the overall study power is estimated to be 80.0% (80.0% = 99.6%[GMTs] x 80.10%[SC rate]).

As shown above, to keep the overall study power of 80%, the sample size was increased accordingly, to have an overall type II error <20% for the 8 NI tests.

Assuming an attrition rate of approximately 10% in this age group, a total of approximately 1334 participants 9 to 49 years of age will be enrolled.

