3.4.4 Exploratory Endpoints

The immunogenicity parameters will be calculated with their 95% CIs using the exact binomial distribution (Clopper-Pearson method) for proportions and using normal approximation of log-transformed for GMTs. All analyses will be conducted by study group. The main parameters will also de described by age subgroup. For some parameters (eg. GMTs, 4-fold rise) difference or ratio between groups may be calculated with 95%CI. The 95% CI of ratios of GMTs will be calculated using normal approximation of log-transformed titers and those for proportions difference (ie, 4-fold rise) will be calculated using Wilson Score method without continuity correction.

Neutralizing Ab titers will be measured for each influenza strain with the SN method.

In particular, the following endpoints will be described with 95% CIs:

- GMTs of individual SN antibody (Ab) titer on D01 and 28 days after vaccination (D29)
- GMs of individual SN Ab titer ratio (fold increase in post-vaccination titer relative to D01) at 28 days after vaccination (D29)
- Percentage of participants with SN Ab titers \geq 20 (1/dil), \geq 40 (1/dil), \geq 80 (1/dil) at 28 days after vaccination (D29)

• Percentage of participants with fold-increase in SN Ab titer (post/pre) ≥ 2 and ≥ 4 at 28 days after vaccination (D29)

SAP Core Body: VAP00027

- Percentage of participants with detectable SN Ab titer (SN Ab titer ≥ 10 [1/dil]) at D01 and 28 days after vaccination (D29)
- The RCDCs of pre-vaccination titer (D01) and post-vaccination titer (D29) will be generated for each study group. The RCDCs will include the plots of the 2 groups on the same figure.

In addition, the descriptive summary of SN immunogenicity results will also be produced by:

- Serological SN status at baseline (< 10 and ≥ 10 1/dil)
- Previous influenza vaccination status
- Age subgroup
- Sex
- Race

The analysis will be conducted for each immunogenicity variable on the PPAS subset (PPAS-SN) and on the FAS subset (FAS-SN) if the attrition rate from FAS-SN to PPAS-SN is greater than 10%.

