4.2.4.3 Duration of the Study

The duration of the study is computed in days as follows:

• Maximum (Visit dates, Termination date, safety follow-up date) – minimum (V01 date) + 1

The duration of the active phase of the study is computed in days as follows:

• Maximum (latest date of V02, latest date of termination during the active phase) – minimum (V01 date) + 1,

The duration of the D181 safety follow-up phase of the study is computed in days as follows:

• Maximum (date of D181 safety follow-up) – minimum (V02 dates, termination dates during the active phase) + 1.

5 Changes in the Conduct of the Trial or Planned Analyses

All analyses planned to be conducted after the interim analysis defined in section 3.5 are strictly descriptive.

SAP Core Body: VAP00027

If the study Team decides not to conduct this interim analysis as defined in section 3.5 and proceed with the completion of the collection of all safety (6 month-follow-up) data through the end of the study; no amendment of this SAP will be written regarding the non-conduct of this interim analysis (section 3.5).

This decision by the study Team would not affect the primary objective of this study and would not require an amendment of characteristics of any of the analyses defined and planned in this study, such as an adjustment of type I and type II errors.

Discarding the interim analysis at D29 from this study, will be reported in only the protocol amendment, and no amendment of this SAP will be written regarding the non-conduct of this interim analysis.

Additionally, blood visit window is increased at statistical analysis level to address operational constraints whilst maintaining clinical relevance of the immunology read-outs.

Moreover, the recruitment of children and adolescents from 9 to 17 years was revealed harder than the recruitment of adults from 18 to 49 years. Hence, the last adult was enrolled on January, 5th 2023, whereas last participant from 9 to 17 years was enrolled on April, 28th 2023.

To assess the impact of this delay in recruitment of participants from both age groups, a complementary analysis will be performed by describing the main immunogenicity endpoints in the period where participants from both age groups were enrolled (i.e., with all participants with D01 date until January, 5th 2023).

SAP Core Body: VAP00027

6 Supporting Documentation

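### The SAP makes the FAS and FAS-SN immunogenicity analyses conditional on more than 10% attrition; the protocol plans them unconditionally and the SAP does not declare the change

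*SAP*

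**What the plan says.** Protocol 9.4.3, for the secondary HAI endpoints: "The analysis will be conducted for each immunogenicity variable on the PPAS and on FAS". Protocol 9.4.4, for neutralization: "The analysis will be conducted for each immunogenicity variable on the PPAS subset (PPAS-SN) and on the FAS subset (FAS-SN"). Neither sentence carries a condition.

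SAP 3.4.3 runs the HAI analysis "on the PPAS, and on FAS if the attrition rate from FAS to PPAS is greater than 10" percent. SAP 3.4.4 plans the PPAS-SN and adds the FAS-SN only "if the attrition rate from FAS-SN to PPAS-SN is greater than 10" percent. The SAP does not say whether the rate is computed over both age groups together or in each.

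The protocol also says what the SAP is for. Section 9: "In accordance with the protocol, the SAP will describe all analyses to be performed by the Sponsor". Section 9.4: "it will include a more technical and detailed description of the statistical analyses described in this section".

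SAP section 5 is the place for changes to planned analyses. It covers the optional interim analysis, the sampling window ("Additionally, blood visit window is increased at statistical analysis level to address operational constraints") and the complementary analysis prompted by slower pediatric recruitment. It says nothing about the FAS.

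**The concern.** A condition that can remove a planned analysis is more than technical detail. Protocol 9.3 lets the SAP refine the PPAS exclusion criteria, and 9.4 lets it elaborate the methods. Neither lets it make an analysis set optional.

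The set matters because the non-inferiority comparison is open-label and non-randomized, and because SAP 3.3 allows the clinical team to add PPAS exclusions during data review (in exceptional circumstances). The FAS output would show whether excluding those participants moves the titers or seroconversion (SC) rates. Protocol 9.4.1 summarises protocol deviations by group. That would reveal unequal exclusion counts, but not their effect on the response.

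**Working it through.** **Inputs.** SAP 3.2: 1200 evaluable (600 per group), approximately 10% attrition, 1334 enrolled, SC rate 50% for two strains and 70% for A/H1N1, SC margin 10 points. SAP 3.4.2: 95% interval for the SC difference by the Wilson score method without continuity correction (Newcombe). SAP 2: at least 400 in the SN subset.

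**1. The plan's own figure.** 600/0.9 = 666.7, rounded up to 667 per group, so 1334. It reproduces. The planned loss is 1334 − 1200 = 134.

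**2. Would the trigger be met?** The planned 10% runs from enrolled to evaluable. The FAS already requires a post-vaccination sample, so FAS-to-PPAS attrition is only part of it. Let m be the number lost with no such sample (the documents give no split, so m is assumed) and take the PPAS as 1200. Attrition = (134 − m)/(1334 − m).

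| m | Attrition | Above 10%? |
|---|---|---|
| 0 | 134/1334 = 10.04% | yes, barely |
| 1 | 133/1333 = 9.98% | no |
| 20 | 114/1314 = 8.7% | no |
| 40 | 94/1294 = 7.3% | no |
| 67 | 67/1267 = 5.3% | no |

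**3. Pooled reading.** 133/1334 = 9.97% does not trigger. If all 133 are in one age group, 133/667 = 19.9% of that group is excluded with no FAS output. In the SN subset, more than 40 of 400 must be excluded.

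**4. How far could FAS and PPAS results differ?** The plan makes no non-inferiority decision on the FAS, so the SC margin serves here only as a yardstick. Lower limit = d − √[(p_c − l_c)² + (u_a − p_a)²], where d = p_c − p_a (children minus adults) and l and u are Wilson limits. Assume 66 excluded per group (66/666 = 9.9%), adults at 50% in both sets, and excluded children g points below PPAS children. The FAS difference is then d − (66/666)g.

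- PPAS, 600 per group: the lower limit reaches −10% at d = −4.39 points.
- FAS, 666 per group: it reaches −10% at a PPAS difference of −3.68 (g = 10) or −4.18 (g = 5).
- Example at d = −4: PPAS limit −9.61%; FAS limit −10.31% (g = 10) or −9.82% (g = 5).
- Chance that the observed PPAS difference falls between the two boundaries when the true difference is 0, with SE = √(2 × 0.25/600) = 2.89 points: 3.7% per strain (g = 10) or 1.0% (g = 5).

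**5. Reversal from an observed PPAS difference of zero (SC 50%).**

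- 66 excluded per group: FAS limit −8.31% at a 30-point gap and −10.28% at 50 points. It crosses −10% at 47.2 points.
- 133 of 667 children and no adults excluded: −9.31% at a 20-point gap and −11.29% at 30 points. It crosses at 23.5 points.

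**The case against.** The strongest objection is that no decision depends on the FAS. The PPAS is the only primary set in both documents, the secondary objectives test no hypothesis, and the SN work is exploratory. This stands, and it limits the point to supportive output.

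The disagreement figures in step 4 use exclusion at the ceiling, whereas step 2 argues that attrition would be lower. This is also fair. With 33 excluded per group (33/633 = 5.2%), the 3.7% and 1.0% fall to 1.8% and 0.5%. At an SC rate of 70% with 66 per group they are 2.8% and 0.8%. The gaps are assumed, and the step 5 figures are bounds rather than expectations.

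The documents give no expected FAS-to-PPAS rate, so whether the trigger is met cannot be settled from them. True, but on the planned loss it is met only at m = 0. The wider window in SAP 3.3 (D26 to D39, against D29 −2/+7 days in the protocol) makes exclusion rarer still, although it also narrows the contrast between the sets.

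A single pooled rate is the natural reading, since each set is defined once across both age groups. Perhaps so, but that is the reading that tolerates heavy exclusion in one group.

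The complementary analysis in SAP section 5 might include participants outside the PPAS. It names no analysis set and covers only enrollment up to 5 January 2023, so it does not replace the FAS. The FAS itself preserves no randomization and does not address missing D29 samples. It shows only the effect of PPAS exclusions among those sampled.

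**Conclusion.** The point holds and should be fixed. The SAP makes two protocol-planned analyses conditional, and the section meant for changes does not say so. On the planning figures the FAS output would probably not be produced. That judgement assumes a PPAS of about 1200 and at least one lost participant without a post-vaccination sample.

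The consequence is limited. The primary decision, sample size, alpha and power are unaffected. Under the assumed 5- and 10-point gaps, the chance of the two sets falling on opposite sides of the SC margin is at most about 4% per strain when true PPAS rates are equal. What is lost is the ability to show that PPAS exclusions did not drive the result. The FAS-SN part has no bearing on non-inferiority; it belongs here because the same undeclared condition was added.

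**What to change.** In SAP 3.4.3 delete the clause that makes the FAS conditional on attrition, and in 3.4.4 delete "if the attrition rate from FAS-SN to PPAS-SN is greater than 10" percent, so that both sets are always analysed as the protocol plans.

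Add one sentence to 3.4.3: FAS GMT ratios and SC differences with 95% CIs are shown beside the PPAS results as supportive, with the number of and reasons for PPAS exclusions by age group. This goes beyond the protocol wording. It is useful because 3.4.3 gives interval methods for the SC difference and the GMT ratio, but its list of displayed statistics names no between-group comparison.

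Declaring and justifying the condition in section 5, with the rate defined, would cure the silence but could still lose the output.

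Cost: two deletions, one added sentence and a second run of existing programs. No new data are needed, and no protocol amendment, because the SAP returns to the protocol text.
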